#### 6.5 WITHDRAWAL/PREMATURE DISCONTINUATION OF STUDY SUBJECTS

Subjects may withdraw from the Study at any time upon written request, or they may be withdrawn at any time at the discretion of the Investigator or Sponsor for safety or administration reasons.

# Subject Discontinuation by Investigator

An Investigator may discontinue a Subject from the Study, with or without the Subject's consent, for any reason that may, in the Investigator's opinion, negatively affect the well- being of the Subject.

# Withdrawal by Subject

If a Subject chooses to withdraw from the Study and also withdraws consent for disclosure of future information, no further evaluation(s) will be performed, and no additional data will be collected. The Sponsor may retain and

FLARE-FT2 Study CONFIDENTIAL Page 34 of 60 continue to use any data collected prior to the withdrawal of consent, unless specified by the Subject or legally authorized representative.

The reason for, and date of, withdrawal must be recorded on the patient's Study Exit CRF. If the reason for the withdrawal is a device-related or procedure-related AE, the event must be reported to the Sponsor and recorded in the CRF.

# 7 RISK AND BENEFIT ANALYSIS

A risk analysis according to ISO 14971 (Application of Risk Management to Medical Devices) has been conducted. Risks have been minimized or eliminate through appropriate design and confirmed by pre-clinical bench, laboratory, and animal testing.

The FlowTriever2 Catheter provides a means for the removal of pulmonary emboli to facilitate the restoration of circulation to the pulmonary vasculature by minimally invasive means. Alternative therapies to endovascular clot retrieval in the treatment of pulmonary embolism include anticoagulation, thrombolytic therapy (systemic or catheter-directed), pharmacomechanical catheter-directed thrombolysis, catheter intervention, and surgical thrombectomy.

Anticoagulation therapy has bleeding risks and a slow onset of action. Thrombolytic therapy has a risk of major hemorrhage, including the risk of hemorrhagic stroke, that may negate the potential benefit derived from this therapy and is not available to patients with absolute and relative contraindications to its use. As with anticoagulation therapy, thrombolytics' onset of action is prolonged.

Pharmacomechanical catheter-directed devices may allow lower dosages of thrombolytics but are nevertheless not appropriate or effective in certain patient populations. Catheter interventions have not been studied in a trial with anticoagulation alone and are often used in combination with thrombolytics. Open surgical embolectomy is a highly invasive surgical technique with a significant mortality rate.

The goal of the FlowTriever2 Catheter is the safe and expeditious removal of the obstructing thrombi from the pulmonary arteries to facilitate right ventricular recovery.

# 7.1 ANTICIPATED RISKS

A risk analysis according to ISO 14971 (Application of Risk Management to Medical Devices) has been conducted. Risks have been minimized or eliminated through appropriate design control, and confirmed by pre-clinical bench, laboratory and animal testing.

# 7.1.1 RISKS DURING THE INTERVENTIONAL PROCEDURE

Possible complications may occur during an interventional procedure. These complications include but are not limited to the following:

- Access site hematoma
- Adverse reaction to device materials
- Aneurysm
- Angina
- Air embolism
- Arrhythmias
- Arteriovenous fistula
- Bradycardia
- Cardiac tamponade
- Cardiogenic shock
- Cardiac Perforation
- Death
- Distal embolism
- Drug reaction to contrast, thrombolytic or anticoagulation
- Embolism
- Fever
- Foreign body embolism

- Fistulation
- General discomfort, tenderness or pain
- Hemoglobinuria
- Hemolysis
- Hemoptysis
- Hypo/Hypertension
- Hypoxemia
- Infection
- Inflammatory response
- Myocardial infarction
- Nausea/vomiting
- Neurological deficit
- Organ impairment
- Pericardial effusion
- Perforation of pulmonary arteries
- Peripheral nerve damage
- Pneumothorax
- Pseudoaneurysm

- Pulmonary edema
- Pulmonary infarction
- Renal failure
- Respiratory failure
- Retroperitoneal hemorrhage
- Right bundle branch block
- Stroke/transient ischemic attack

- Tachycardia
- Valvular disruption/injury
- Vascular spasm
- Vasovagal reaction
- Ventricular rupture
- Vessel dissection/perforation
- Vessel stenosis

#### 7.1.2 DEVICE WARNINGS

The following warnings are labeled for the FlowTriever2 Catheter:

- Intended for single use only.
- Do not re-sterilize or reuse this device
- Should be used in conjunction with fluoroscopic guidance and proper anticoagulation agents.
- Examine the catheter before use to verify it is not damaged.
- Use before the "Use By" date specified on the product packaging.
- Avoid using excessive force to advance or retract against resistance. If excessive resistance occurs, retract
  and collapse the distal element into the catheter and remove the device. Excessive force against resistance
  may result in damage to the device or vessel perforation.
- In the event of patient deterioration, remove FlowTriever2 Catheter/Triever device and assess situation.
- Ensure that FlowTriever2 element is withdrawn into Triever Catheter prior to removal from patient to avoid vascular damage.
- Do not use in blood vessels that have a history of therapeutic irradiation. Vessel perforation may occur.

#### **7.1.3** RISKS OF CT

- High radiation exposure in cases of repeated examinations; possible increase in risk of cancer
- Rise in serum creatinine levels
- Nephropathy

## 7.1.4 POTENTIAL RISKS OF THE PROPOSED INVESTIGATION

The risks associated with the FlowTriever2 Catheter are on the order of coronary endovascular interventions and catheter-directed embolectomies. Potential risks and complications include those resulting from anticoagulation and contrast dye, including bleeding, contrast-induced nephropathy, and anaphylactic reactions to iodine contrast. Potential vascular access complications include bleeding, hematoma, arteriovenous fistula, and pseudoaneurysm. The most serious complication resulting from catheter-directed procedures is perforation or dissection of a pulmonary artery, causing massive pulmonary hemorrhage and immediate death. The risk of perforation increases with smaller vessels. Other serious complications include pericardial tamponade, pneumothorax, cardiac rupture and cardiac arrest. Transient, periprocedural complications include arrhythmias when the catheter advances through the right heart, right heart block or bradycardia, worsening hypoxemia, and hemodynamic deterioration. The above risks are no greater with the use of the FlowTriever2 Catheter than that of any coronary endovascular intervention or catheter-directed embolectomy procedure.

Malfunction of the device could result in cardiac damage and artery dissection/perforation of the artery; these are thought to be the most severe complications associated with the FlowTriever procedure. Manufacturing controls are in place to ensure consistent product quality and to minimize defective devices entering distribution.

Under fluoroscopic guidance, the device is tracked over the guidewire into the pulmonary artery to the site of the pulmonary emboli. Use of fluoroscopic guidance for vascular access minimizes the risk of access failure and

FLARE-FT2 Study CONFIDENTIAL Page 37 of 60

vascular complications, such as vessel perforation and vessel trauma. To further minimize the risk of perforation or dissection, the FlowTriever2 Catheter will only be used in the main and lobar pulmonary artery branches and will not be attempted in smaller vessels (< 6 mm diameter).

Mechanical thrombus retrieval from the pulmonary arteries can, in theory, result in dispersion of some residual thromboembolic material distal to the central obstruction to the periphery of the lungs. With fragmentation devices, the fundamental objective is to eliminate central thrombi and fragment them so that they migrate to more distal branches, thus alleviating main pulmonary obstruction, which allows both an improved perfusion and a reduction of elevated pulmonary arterial pressures right ventricular pressure overload. Worsening of hemodynamic parameters due to distal embolization can occur, however, available clinical data does not associate serious adverse sequelae due to distal embolization in PE patients treated with fragmentation devices. Since the primary mode of action of the FlowTriever2 Catheter is clot retrieval, the potential for distal showering of thromboemboli does exist, but with the synchronized thrombus removal mechanism of the FlowTriever2 Catheter and aspiration capability of the Triever Catheter, it is anticipated to occur less frequently and to a lesser degree than devices that rely solely upon fragmentation. The minimal risk of distal embolization is outweighed by the anticipated benefits of the FlowTriever2 Catheter in the acute relief of the pulmonary arterial emboli.

Finally, while the intent of FlowTriever2 intervention is not to remove the entire embolic load, the risk of clot remaining after the embolectomy procedure is mitigated by the physician's ability to deliver thrombolytic to enhance both the impact of clot extraction and the body's natural lytic system. Future thrombolytic therapy is not precluded following FlowTriever2 treatment.

## 7.2 RISK MITIGATION

Awareness of the potential for serious complications is essential to the safe use of the FlowTriever2 Catheter. Additional risk mitigations include:

- Careful patient selection based on study inclusion/exclusion criteria,
- Use of study sites that have sufficient expertise and resources to manage adverse events and provide appropriate additional therapies if needed,
- Specialized/experienced Investigators with appropriate training,
- Timely reporting of adverse events,
- Independent Clinical Events Committee, and
- Informed consent process.

#### 7.3 POTENTIAL BENEFITS

There are no guaranteed benefits from participation in this study. In general, endovascular interventions (e.g., catheterization) are well-established in medical practice and are substantiated to minimize the risks to patients of: anesthesia complications, wound healing, bleeding and infection. The tissue and other bodily trauma associated with open surgical procedures are much greater compared to minimally invasive techniques. As more tissue is exposed to air in an open surgical procedure, the risk of infection is greatly increased. As such, the medical option of an open surgical procedure is far inferior to the safer, less traumatic, endovascular procedure. The reduced tissue trauma may benefit the subject by reducing pain as well as faster recovery time. By minimizing tissue manipulation, the FlowTriever System may also benefit medical practice by reducing the operative time offering potential cost savings.

Systemic administration of thrombolytic agents carries significant risk of bleeding, especially when predisposing conditions or comorbidities exist. Disruption of the emboli by the FlowTriever2 Catheter may enhance the effectiveness of thrombolytic agents by providing greater surface area contact of the therapeutic agent with the embolic mass. The aspiration of the emboli from the vasculature minimizes the potential for re-thrombosis and/or new emboli formation.

Information gained from the conduct of this Study may be of benefit to other persons with the same medical condition.

### 7.3.1 POTENTIAL BENEFITS OF THE PROPOSED INVESTIGATION

Endovascular interventions (e.g. catheterization) are well-established in medical practice and are substantiated to minimize the risks to patients, including: anesthesia complications, wound healing, bleeding, and infection. FlowTriever intervention has an immediate impact on the vascular obstruction. The FlowTriever intervention is not reliant on the use of thrombolytics and therefore the FLARE-FT2 trial does not exclude patients with recent surgeries nor those at a high risk of catastrophic bleeding.

### 7.3.2 ASSESSMENT OF UNCERTAINTY

There is a low degree of uncertainty regarding anticipated benefits of the clinical study since any amount of thrombus removal should be beneficial to the patient.

#### 7.4 ALTERNATIVE TREATMENTS

There is no obligation for a Subject to take part in this Study. Alternative treatments may include:

- Medical Therapy: Includes the use of anticoagulation therapy alone and/or systemic thrombolytics.
- Catheter-Directed Therapy: Pharmacomechanical delivery of intrapulmonary thrombolytics, with or without ultrasound assistance.
- **Mechanical Thrombectomy Device:** An alternate FDA cleared catheter-based device designed to remove, fragment or dissolve blood clot.
- **Surgical Embolectomy:** Surgical removal of the pulmonary embolism.

The Investigator will inform the Subject as to what alternative methods are suitable and available.

# 8 ADVERSE EVENT AND PRODUCT COMPLAINT RECORDING/REPORTING

Subject safety is of the utmost importance. Each Investigator has the responsibility for the safety of the subjects under his/her care. For purposes of understanding data and relevant confounders, assessment of clinical outcomes and/or SAEs possibly related or probably related to PE condition or complications thereof will be recorded.

### 8.1 COMPLICATIONS

Complications should be reported on a per-subject basis and categorized according to the SIR Classification of Complications by Outcome as follows:

- Minor Complications
  - No therapy, no consequence
  - Nominal therapy, no consequence (includes overnight admission for observation only)
- Major Complications
  - Require therapy, minor hospitalization (≤ 48 hours)
  - Require major therapy, unplanned increase in level of care, prolonged hospitalization (> 48 hours)
  - Permanent adverse sequelae
  - o Death

FLARE-FT2 Study CONFIDENTIAL Page 39 of 60

Inari Medical
FlowTriever2 Catheter

## 8.2 ADVERSE EVENTS (AE)

An Adverse Event (AE) is any untoward medical occurrence, unintended disease or injury, or untoward clinical signs (including abnormal laboratory findings) in subjects, users or other persons, whether or not related to the investigational medical device and whether anticipated or unanticipated. (ISO 14155:2020 3.2)

- **NOTE 1:** This definition includes events related to the investigational medical device or the comparator.
- **NOTE 2:** This definition includes events related to the procedures involved.

**NOTE 3:** For users or other persons, this definition is restricted to events related to investigational medical devices or the comparator.

Disease signs and symptoms that existed prior to study participation are not considered AEs unless the condition recurs after the subject has recovered from pre-existing condition, or the condition worsens in intensity or frequency during the study.

Collection of adverse events will start after the time that informed consent form is signed and subject is enrolled. Adverse events will be monitored throughout the study. Investigators must obtain all information available to determine the causality and outcome of the AE and to assess whether it meets the criteria for classification as a serious adverse event requiring immediate notification to the Sponsor or its designated representative. All reported AEs will be documented on the appropriate CRF and will include the event description (sign, symptom, or diagnosis), onset, resolution, seriousness, severity, cause and action taken. The Investigator must assess causality and severity for all AEs.

All AEs will be followed by the Investigator until resolution or until the 30-day follow-up visit.

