# 2.2 OPERATING PRINCIPLE

The FlowTriever2 Catheter provides a mechanical means for the retrieval of blood clots, which can then be aspirated using the Triever Catheter, from the vasculature. These features facilitate the reperfusion of vasculature obstructed by acute clot.

The system is designed for use with a 0.035" guidewire. The outside diameter of the Triever Catheter is available in 16 Fr, 20 Fr, and 24 Fr sizes. The outside diameter of the FlowTriever2 Catheter is 17 mm.

An introducer sheath is used to access the appropriate vessel and place the 0.035" guidewire through and past the clot under fluoroscopic guidance. The Triever Catheter with dilator is then introduced over the guidewire and situated on the proximal side of the clot. The tip of the dilator and Triever Catheter contain radiopaque markers for fluoroscopic positioning. The dilator is removed from the Triever Catheter, and the FlowTriever2 Catheter is placed over the guidewire, through the Triever Catheter, and is passed through the clot. The delivery catheter component of the FlowTriever2 Catheter is retracted, causing the self-expanding wireform component of the FlowTriever2 Catheter to expand within the blood vessel distal to, and within, some portion of the clot. Expansion of the device may allow some blood flow to be restored. The proximal end of the self-expanding wireform contains a radiopaque marker to aid in maintaining proper position. The FlowTriever2 Catheter can be manually retracted into the Triever Catheter, and simultaneous aspiration of fluid and clot can be performed through the Triever Catheter using a provided large-bore syringe. The device with captured clot is removed from the body.

[figure not shown]
Pulmonary embolisms are caused by clots that typically originate in the leg in the form of a cast of the vessel from which they broke loose. The clots tend not to be the same diameter of the pulmonary artery. They travel en masse and often fold upon themselves, and/or collect together in the pulmonary artery, giving the appearance of a large clot. Retrieving the clot is similar to grabbing the head of the snake and pulling in the rest of the clot (body) as with retraction and aspiration. The elasticity of the clot, depending on its age, and various other factors, make it soft enough to deform during the retrieval process and fit into the Triever Catheter.

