# 4.2 PRIMARY ENDPOINT - SAFETY

The study's primary safety endpoint is incidence of adjudicated Serious Adverse Events (SAE), which is a composite of:

- Mortality through 48 hours after the index procedure related to FlowTriever2 Catheter
- Major bleeding through 48 hours after the index procedure related to FlowTriever2 Catheter
- Intra-procedural device or procedure-related adverse events, including:
  - Clinical deterioration defined by hemodynamic or respiratory worsening
  - Pulmonary vascular injury related to FlowTriever2 Catheter
  - Cardiac injury related to FlowTriever2 Catheter

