### 5.3 STUDY POPULATION

The study population consists of subjects that have a PE. Subject eligibility is to be determined based on data available to the Investigator at the time of enrollment. Subjects must meet all inclusion and no exclusion criteria to be eligible for the study. Waivers will not be granted by the Sponsor regarding enrollment criteria. All subjects that complete the procedure and the follow-ups will be included in the analysis.

In this study, subjects will be categorized as follows:

**Screen Failure:** Any screened patient who does not meet the inclusion and exclusion criteria. No case report forms (CRFs) are required for these patients. All patients screened will be documented on the Screening/Enrollment Log.

**Enrolled Subject:** All patients who met the inclusion/exclusion criteria and in whom the FlowTriever2 Catheter is inserted into the vasculature. These subjects will comprise the "Enrollment Population."

**Intent-To-Treat (ITT):** All "Enrolled Subjects" in whom the procedure was attempted and the FlowTriever2 Catheter was deployed, whether successful or not.

**Modified Intent-To-Treat (mITT):** All subjects in the "ITT Population" who have no thrombolytics administered during the procedure.

**Full Analysis Set (FAS):** All subjects in the "mITT Population" that have successfully received the procedure and have completed the 48-hour post- procedure follow-up (+36 hours or discharge, whichever comes first) per study protocol.

**Completed Cases (CC):** All subjects in the "mITT Population" that have successfully received the procedure and have completed all follow-up visits.

FLARE-FT2 Study CONFIDENTIAL Page 26 of 60

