### 5.4 STUDY ENROLLMENT CRITERIA

Only patients who meet all inclusion criteria and none of the exclusion criteria are considered eligible for enrollment. The decision to use the FlowTriever2 Catheter will occur prior to the procedure and written informed consent will be obtained prior to all study-specific procedures.

If the FlowTriever2 Catheter is not inserted into the vasculature, the subject is considered a screen failure (not meeting inclusion criteria for use of FT2) and is not enrolled nor entered into the EDC.

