# 6.2.1 BASELINE

Baseline assessments will include the following:

- Verification of inclusion/exclusion criteria
- Medical history
- Physical examination/vitals
- Blood labs
- CT angiography to confirm PE and RV/LV ratio for inclusion
- Concomitant medications

**Medical/Surgical History:** Relevant medical and surgical history will be collected from all consented subjects at the time of enrollment.

**Blood Labs**: The following blood values must be available to assess Subject eligibility for the study and for baseline data collection: hematocrit, hemoglobin, platelet count, serum creatinine, and International Normalized Ratio (INR).

**Concomitant Medications**: It is required that the subject's relevant concomitant medication use during the study be documented at pre-procedure, procedure, and follow- up visits.

FLARE-FT2 Study CONFIDENTIAL Page 31 of 60

\*\*Day 0 is the date of the FlowTriever procedure, Time 0 is when the FlowTriever2 Catheter enters the vasculature

\*\*\* Anticoagulation and Thrombolytics

\*\*\*\*If discharged prior to 48 hours from Index Procedure, phone call to subject will be conducted to confirm if any SAEs occurred between time of discharge and 48 hours.

As part of the routine care to treat PE, anticoagulation medication is administered to impede blood clotting and thrombolytic medication may be administered to dissolve blood clots. The specific dose and course of administration is at the discretion of the Investigator and will be recorded on the case report form (CRF).

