#### 8.5 ADVERSE EVENT REPORTING

Subjects will be carefully monitored during the study for possible adverse events. Any adverse event that occurs after the time of informed consent and a study specific exam or procedure through end of study participation will be fully evaluated by the Investigator. Appropriate treatment will be initiated, and the study follow-up will continue as completely as possible.

The Investigator will document all observations and clinical findings of adverse events, including the nature, severity and relationship, on the appropriate CRFs.

The Investigator is required to report all UADEs/USADEs to the Sponsor within 24 hours after first learning of the event, and all SAEs within 5 business days after learning of the event. The Investigator must follow their local IRB policy for SAE/UADE/USADE reporting.

The Investigator will send the completed SAE Report form and all available supporting documentation to the Sponsor.

As additional information becomes available, the Investigator will record all adverse events (serious and non-serious), adverse device effects (anticipated and unanticipated), device malfunction, product complaints or other reportable safety events on the appropriate CRFs. Copies of source documentation which contain significant information related to the event such as progress notes, consultations, nurse's notes, operative reports and patient summaries etc. are required for evaluation of the event. Copies of such documentation shall be obtained from the Investigator (de-identified as to the Subjects' identity) and provided to the Sponsor.

Regarding subject deaths, it is requested that a copy of the death certificate and a copy of the autopsy report, if applicable, be sent to the Sponsor when available. Any other source documents related to the death should also be provided to the Sponsor. In the event that no source documents are available, the PI is required to describe the circumstances of the Subject's death in a letter, e-mail or other written communication.

UADEs/USADEs have special reporting requirements. The Sponsor will notify the sites, IRBs and regulatory bodies as per specific regulations.

In addition, the Sponsor will comply with Medical Device Reporting (MDR) requirements.

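### Adverse-event collection has no single start point; read literally, protocol section 8.2 omits procedure-related clinical deterioration that occurs before FlowTriever2 entry in subjects who are then enrolled

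*Protocol*

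**What the plan says.** Four places in the protocol bear on when adverse events start to count.

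- **Section 8.2** gives an explicit start: "Collection of adverse events will start after the time that informed consent form is signed and subject is enrolled".
- **Section 5.3** defines enrolled subjects: "All patients who met the inclusion/exclusion criteria and in whom the FlowTriever2 Catheter is inserted into the vasculature". Inclusion criterion 9 in section 5.5 repeats the condition, and section 5.4 gives the converse: "If the FlowTriever2 Catheter is not inserted into the vasculature, the subject is considered a screen failure". The Table 1 footnotes place the study clock at the same moment: "Time 0 is when the FlowTriever2 Catheter enters the vasculature".
- **Section 8.5** covers a different span: "Any adverse event that occurs after the time of informed consent and a study specific exam or procedure through end of study participation". It does not mention enrolment and does not say which exam or procedure is meant.
- **Table 1 and section 6.2.2** list adverse events among the items recorded at the procedure on Day 0. Day 0 is a date, and neither place gives a start time within it.

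The primary safety composite (protocol 4.2 and 9.3, SAP 2.1) contains this limb: "Intra-procedural device or procedure-related adverse events, including" clinical deterioration, pulmonary vascular injury and cardiac injury. The last two must be related to FT2, as must 48-hour mortality and 48-hour major bleeding. Clinical deterioration carries no such condition. Neither document says when the intra-procedural period begins. The SAP has no rule of its own on when collection starts.

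**The concern.** A good part of the intervention takes place before FT2 is in the body. Under section 8.2, an unplanned intubation or a need for vasopressors in that part falls before collection starts, even if the subject goes on to receive FT2 and is analysed. Under another section of the same protocol, the event may well be recorded. The composite is meant to count procedure-related clinical deterioration whichever device was in use, so the start rule can change the primary safety count.

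Such a loss can only lower the reported rate. Adjudication cannot repair it, because the Clinical Events Committee (section 8.7) reviews events that have been collected. The affected limb is not a marginal one. Protocol section 3.1 reports that in the predecessor study (FLARE) all four patients with a major adverse event had clinical deterioration, and that every such event was judged procedure-related and none device-related.

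**Working it through.** **1. The plan's own figure.** Protocol 9.1 and SAP 5.1 give N = 50, an assumed event rate of 11%, a performance goal of 25%, one-sided alpha 0.05 and power of at least 80%. With X binomial:

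- P(X ≤ 7 | 50, 0.25) = 0.0453 and P(X ≤ 8 | 50, 0.25) = 0.0916, so the exact rule would be at most 7 events.
- P(X ≤ 7 | 50, 0.11) = 0.8207, so power is 82.1%. A normal approximation gives 81.3%.

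The stated power reproduces. The present point does not depend on it.

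**2. Order of events.** From protocol 2.2, 6.1.4 and 6.2.2:

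| Step | Before FT2 entry? | Collected under 8.2? | Covered by 8.5? |
|---|---|---|---|
| Sedation or anesthesia | yes | no | depends on the undefined exam or procedure |
| Venous access, guidewire into the pulmonary artery | yes | no | depends, as above |
| Baseline invasive pulmonary artery pressure | yes | no | from here at the latest, if this counts as study-specific |
| Triever placement | yes | no | as the row above |
| FT2 through the Triever (enrolment, Time 0) | – | yes | yes |

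On the Triever step, section 2.2 says: "The Triever Catheter with dilator is then introduced over the guidewire and situated on the proximal side of the clot". FT2 then passes through the Triever already in place. The pressure reading is taken once access has been achieved (section 6.1.4). If that reading is the study-specific procedure meant in 8.5, events during access fall outside 8.5 as well.

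**3. Which components can be affected.**

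| Component | Must be related to FT2? | Can an event before FT2 entry count? |
|---|---|---|
| Mortality to 48 h | yes | no |
| Major bleeding to 48 h | yes | no |
| Clinical deterioration | no | yes |
| Pulmonary vascular injury | yes | no |
| Cardiac injury | yes | no |

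This treats the three listed intra-procedural items as the full list. The definition in protocol section 12 narrows the exposure further. Its listed examples include unplanned intubation or ventilation, hypotension that is prolonged or needs vasopressors, shock, resuscitation and persistent worsening of oxygenation. Arrhythmia alone is not among them.

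**4. Size.** One affected subject is 1/50 = 2 percentage points, provided that subject has no other qualifying event. The exact one-sided 95% upper limit is the 0.95 quantile of Beta(x + 1, 50 − x):

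- 2/50 = 4%, upper limit 12.1%
- 1/50 = 2%, upper limit 9.1%

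The documents give no share of events occurring before FT2 entry. The shares below are assumptions, and recorded rate = true rate × (1 − share lost):

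| Assumed share lost | True rate 3.8% (FLARE) | True rate 11% (planning) |
|---|---|---|
| 0% | 3.8% | 11.0% |
| 10% | 3.4% | 9.9% |
| 20% | 3.0% | 8.8% |
| 30% | 2.7% | 7.7% |

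**The case against.** **Few subjects can be affected.** The event must meet the deterioration definition before FT2 entry, and the subject must still be enrolled. Section 5.3 judges eligibility on the data available at enrolment. Persistent hypotension, a vasopressor requirement or a high oxygen requirement would conflict with inclusion criterion 6 or exclusion criteria 3 and 4. SAP section 3 removes anyone later found ineligible, and a patient who never receives FT2 is a screen failure. This largely stands, and it is why the number is probably small. It is not zero. A patient may be intubated and remain within the oxygen limit, or a site may settle eligibility before access, as section 6.2.2 allows.

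**Other text points toward capture.** Table 1 and section 6.2.2 call for adverse events at the procedure. A note in section 8.2 includes events related to the procedures involved. Section 8.4 has a category for ancillary devices that names the Triever and the guidewire. All of this shows an intention to record such events, and many sites would do so. None of it displaces the explicit start in 8.2.

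**Stronger readings that the documents do not support.**

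- A reader might infer that vessel or heart injury during access is lost from primary safety. Those components need a relation to FT2, so an injury before FT2 entry would not count under either start rule.
- A reader might infer a false pass against the 25% goal, since 8/50 has an upper limit of 27.0% and 7/50 of 24.7%. SAP sections 2 and 5.1 make the endpoints descriptive, with no success rule, so no test result can change.
- A reader might infer from FLARE that such events are common. Sections 3.1 and 3.2 place no FLARE event before device entry.
- A reader might infer that Time 0 already defines the start of the intra-procedural period. It is a schedule footnote, and nothing links it to the endpoint.
- Bias that differs by site is possible, but the documents do not show that sites follow different sections.

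**Conclusion.** The inconsistency is real and limited in reach. Section 8.2 sets a start at FT2 entry, section 8.5 sets an undefined one that may be earlier, and Table 1 and section 6.2.2 set none. Followed literally, 8.2 omits procedure-related clinical deterioration before FT2 entry in subjects who are then enrolled. No other named component of primary safety is affected.

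The effect is a possible understatement of a descriptive rate, by 2 percentage points for each subject whose only qualifying event is lost. The count is unknown and probably small. The conclusion rests on three assumptions: that enrolled in section 8.2 has its section 5.3 meaning, that the composite's intra-procedural list is closed, and that access and Triever placement belong to the procedure. The point is worth correcting because the error runs in one direction only, touches the main safety result and is cheap to remove.

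**What to change.** - **One start point.** Reconcile sections 8.2, 8.5 and Table 1. For every subject who becomes enrolled, collect adverse events from signed consent, including those before FT2 entry.
- **Define the period.** State in the protocol (4.2, 9.3) and SAP (2.1) that intra-procedural includes the access and Triever placement steps and does not begin at Time 0.
- **Do not copy 8.5 into 8.2.** Its undefined exam or procedure may fall after access, so the gap would remain.

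**Cost.** A few sentences in each document, with no change to sample size, visits or treatment. The reported event count may be slightly higher. The change does not capture patients who deteriorate and never receive FT2, because section 5.4 keeps them out of the database.
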